### 8.2.2 Primary Effectiveness Endpoint

The primary effectiveness endpoint is defined as the freedom from documented atrial fibrillation, atrial flutter and atrial tachycardia (AF/AFL/AT) (hereinafter collectively referred to as "atrial tachyarrhythmias") recurrence (episodes  $\geq$  30 secs on TTM or continuously recorded on the standard 12-leads ECG) during the evaluation period (Day 91-365) and freedom from the following failure modes:

- Acute procedural failure, including:
  - Failure to confirm entrance block in all pulmonary veins post-procedure,
  - Use of a non-study catheter to treat left atrial ablation targets and cavo-tricuspid isthmus
- Repeat ablation failure, including:
  - $\circ$  > 2 repeat ablation procedures with the study catheter during the 3-Month Blanking Period (Day 0-90) after the index ablation procedure.
  - Use of a non-study catheter to treat study arrhythmia ablation targets during the blanking period
  - Any repeat ablation procedure during the Evaluation Period.
- AAD failure: Taking a new AAD for AF or a previously failed AAD at a greater than the highest ineffective historical dose for AF during the evaluation period (refer to section 13.1 for details).

This study is designed to compare the primary effectiveness of the QDOT MICROTM Catheter to a pre-determined performance goal of 50%, which is indicated as the

	Biosense Webster, Inc	
Version 5.0 – Feb 3, 2021	CONFIDENTIAL	

minimum acceptable success rate at 12 months for a paroxysmal AF population in the 2017 HRS/EHRA/ECAS/APHRS/SOLAECE consensus statement.

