### 8.2.3.2 Secondary Effectiveness Endpoints

• Acute Procedural Success

Acute procedural success is defined as confirmation of entrance block in all PVs.

- % of subjects with electrical isolation of PVs (entrance block) at the end of the procedure
  - The % of subjects with electrical isolation of PVs (entrance block) using QMODE+ as only ablation strategy
- % of subjects with electrical isolation of PVs (entrance block) after first encirclement (evaluated prior to the 20-minute waiting period and adenosine challenge
- % of subjects with electrical isolation of all PVs (entrance block) after first encirclement without acute reconnection, after waiting period and adenosine challenge
- % of subjects and % of PVs with touch-up (i.e. touch-up is used to remove ablation of acute reconnection) among all targeted veins and touch-up location
- o Anatomical location of acute PV reconnection after first encirclement
- Repeat ablation procedures during 12-month period post-procedure
  - Incidence (%) of repeat ablation procedures
  - o % PVs re-isolated among all the targeted PVs at repeat procedure
  - % repeat ablation procedures requiring new linear lesions and/or identifying new foci outside of initially isolated area among the repeat ablation procedures
- 12-Month Single Procedure Success

• The 12-month single procedure success is defined as freedom from documented AF/AFL/AT recurrence (episodes  $\geq$  30 secs) during the Evaluation Period after a single ablation procedure and off AADs. Any repeat ablation procedure or AAD therapy will be deemed effectiveness failure for this analysis.

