5 ANALYSIS SETS

The following analysis sets will be used for the Variable Flow study:

- Safety Analysis Set: The Safety analysis set will include all enrolled subjects in the Variable Flow study who have the investigational device inserted, regardless of RF energy delivery.
- Modified Intent-To-Treat (mITT) Analysis Set: The mITT analysis set will consist of all enrolled subjects in the Variable Flow study who meet all eligibility criteria and have the investigational device inserted. Subjects in this analysis set who are discontinued due to reasons related to the QDOT MICROTM catheter will be considered as acute effectiveness failures; subjects who are discontinued due to reasons not related to the QDOT MICROTM catheter will not be considered as acute effectiveness failures.
- **Per Protocol (PP) Analysis Set:** The PP analysis set will include subjects in the Variable Flow study who satisfy the following criteria:
 - Enrolled and meet eligibility criteria
 - Have undergone RF ablation
 - Are treated with the study catheter, and have been treated for the study related arrhythmia
 - without major protocol deviations:
 - Missing all protocol-specified electronic effectiveness monitoring
 - Esophageal monitoring is not done per protocol and risk is not mitigated
 - Not following the required waiting period of 20 minutes before pacing procedures, and/or infusion of cardiac medications to induce AF/reconnection is not performed before entrance block confirmation
 - Undergoing the ablation procedure with a constant flow rate in place of the variable flow rate

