7 STATISTICAL ANALYSIS METHODS

7.1 General Conventions

Standard descriptive summaries for continuous variables will include the number of observations with data, mean, standard deviation, median, 25% percentile, 75% percentile, minimum and maximum values. For categorical variables, the count and percentage will be provided. Percentages will be based on the number of subjects without missing data.

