7.6 Analysis of Primary Effectiveness Endpoint

The primary effectiveness endpoint will be assessed by testing the following hypothesis:

$$H_0: p_E \le 0.50$$
 vs $H_A: p_E > 0.50$,

where p_E is the effectiveness success rate. The mITT Analysis Set is the primary analysis set for the primary effectiveness endpoint.

The primary analysis for the primary effectiveness endpoint will use complete follow-up data from the Variable Flow study with borrowing from the mITT analysis set in the Main study, and apply Bayesian testing using a beta-binomial model.

The primary effectiveness endpoint will be considered as success if

$$\Pr(p_E > 0.5 | x, n) > 0.975$$

where p_E is the 12-month effectiveness rate.

If the posterior probability of the effectiveness rate being greater than 50% is higher than 0.975, then the study will be considered to have demonstrated effectiveness of the device.

The Variable Flow study will be considered achieving study success when both the primary safety and primary effectiveness performance goals are met. The following additional

analyses will be performed at the time of the final effectiveness analysis. Similar to the safety sensitivity analyses, the posterior distribution for the effectiveness endpoint for each stratum is updated by incorporating the missing effectiveness outcomes according to each scenario. Borrowing from the main study remains unchanged from the primary analysis, i.e., sensitivity analyses will be performed for missing primary endpoint data in the Variable Flow study.

• Tipping Point Analysis

Tipping point analysis will be performed for the primary effectiveness endpoint in the mITT analysis set to assess the impact of missing outcomes in the Variable Flow study on the primary effectiveness analysis. The posterior distribution will be updated each time to evaluate whether a tipping point is identified.

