7.7.2 Analysis of Secondary Effectiveness Endpoint

Descriptive statistics will be provided on the following endpoints in the PP analysis set in the Variable Flow study.

• Acute Procedural Success: confirmation of entrance block in all PVs.

The number and percentage of subjects with acute procedural success and the corresponding 97.5% exact binomial lower confidence bound will be presented.

• PV Isolation/ Acute Reconnection/ Touch-Up Application:

• PV isolation at the end of the procedure

Percent of subjects and percent of targeted PVs where PVI was achieved at the end of the index procedure, including additional RF application for the PV reconnection if applicable, will be summarized descriptively.

The achievement of PVI at the end of the procedure will be identified at the following time points, including 1) before the required 20-min waiting period, or 2) after the adenosine challenge was performed, and 3) after additional RF application for PV reconnection, whichever occurs last during the index procedure.

• Rate of PVI achieved at the end of procedure among targeted veins:

= number of targeted veins reaching PVI at the end of procedure total number of targeted veins

• Rate of PVI achieved at the end of procedure among subject:

= number of subjects reaching PVI at the end of procedure total number of subjects undergone ablation procedure

• PV isolation using QMODE+ as only ablation strategy

Percent of subjects and percent of targeted PVs where PVI was achieved at the end of the index procedure by using only the QMODE+ during the procedure will be summarized descriptively.

• Rate of PVI achieved by using QMODE+ only among targeted veins:

= number of targeted veins reaching PVI at the end of procedure by using QMODE + only total number of targeted veins

• Rate of PVI achieved by using QMODE+ only among subjects:

= $\frac{number \ of \ subjects \ reaching \ PVI \ at the \ end \ of \ procedure \ by \ using \ QMODE \ + \ only}{total \ number \ of \ subjects \ who \ underwentablation \ procedure}$

• PVs isolation after first encirclement (evaluated prior to the 20-minute waiting period and adenosine challenge)

Percent of subjects and percent of targeted PVs where PVI was achieved before the required 20-min waiting period, regardless the additional application was applied to remove the PV reconnection or not, will be summarized descriptively.

• Rate of PVI achieved prior to 20-min waiting period among targeted veins:

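### Acute procedural success in the Variable Flow SAP can count a vein completed with a non-study catheter as a success, and its per-protocol set can leave out acute failures that the primary analysis keeps

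*SAP*

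**What the plan says.** **Definition.** SAP 7.7.2 gives "Acute Procedural Success: confirmation of entrance block in all PVs". Protocol 8.2.3.2 agrees: "Acute procedural success is defined as confirmation of entrance block in all PVs". Neither sets a condition on which catheter produced the block.

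**Acute failure in the primary endpoint.** Protocol 8.2.2 lists two components. One is "Failure to confirm entrance block in all pulmonary veins post-procedure". The other is "Use of a non-study catheter to treat left atrial ablation targets and cavo-tricuspid isthmus".

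**Analysis sets.** For the secondary effectiveness endpoints, SAP 7.7.2 states: "Descriptive statistics will be provided on the following endpoints in the PP analysis set in the Variable Flow study". For the primary endpoint, SAP 7.6 states: "The mITT Analysis Set is the primary analysis set for the primary effectiveness endpoint".

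**Who is in each set.** Under SAP 5, PP requires RF ablation and treatment with the study catheter. It excludes subjects with listed major deviations, among them missing all protocol-specified electronic effectiveness monitoring, and "Not following the required waiting period of 20 minutes before pacing procedures" or omitting the drug challenge before entrance block is confirmed. The mITT set needs only eligibility and insertion of the device. Within it, discontinuation for a catheter-related reason is an acute effectiveness failure, and discontinuation for any other reason is not.

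**Status.** SAP 7.7 makes the secondary endpoints descriptive, with no hypothesis. SAP 7.7.2 nevertheless attaches an exact 97.5% lower bound to acute procedural success.

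**The concern.** Acute procedural success is meant to show whether the catheter isolates the veins on the day. Two features let the reported rate depart from that.

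The first is classification. If a vein resists and is finished with another catheter, entrance block is confirmed and the secondary definition is met, while the primary endpoint calls the same procedure an acute failure.

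The second is the denominator. The outcome is settled at the procedure, but membership of PP depends on procedural compliance and on rhythm monitoring obtained later. Some subjects whom the plan itself regards as acute failures cannot be in PP, or may fall out of it.

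At stake is the credibility of a rate and lower bound likely to be quoted when the variable flow configuration is described. A reader who set that rate beside the acute failures within the primary endpoint could find that they disagree.

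**Working it through.** The documents give no expected rate, goal or power for this endpoint, so there is no planned figure to reproduce. The check is to follow types of subject through both rules, then show how far the rate could move.

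**Step 1: subject by subject.**

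| Subject | Primary endpoint (mITT) | Acute procedural success (PP) |
|---|---|---|
| All veins blocked, one finished with a non-study catheter | Acute failure (Protocol 8.2.2) | Success: block confirmed, and PP does not exclude added use of another catheter |
| Catheter inserted, no RF, discontinued for a catheter-related reason | Acute effectiveness failure (SAP 5) | Not in PP, which requires RF ablation |
| Procedure ended with block unconfirmed, before the wait or challenge | Acute failure | Can fall out of PP as a major deviation |
| Wait and challenge done, block not achieved | Acute failure | In PP, not a success |
| Block confirmed but wait skipped, study catheter only | Not an acute failure | Out of PP: a success removed |
| Block confirmed, then no rhythm monitoring at all | Not an acute failure | Out of PP: a success removed |

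The first three rows are where the two endpoints part in the favourable direction. The fourth shows agreement. The last two show exclusions that remove successes.

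The first row is foreseen by the plan: Protocol 13.5 records RF applications made with a non-study catheter. The second follows from Protocol 9.5, where a discontinued subject is one in whom no RF energy was applied. For the last row, Protocol 13.10 supplies the transtelephonic monitor no later than the month 3 visit, so early death or withdrawal can leave a subject with no such monitoring. How the SAP would treat monitoring that was not yet due is not stated.

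**Step 2: size.** Inputs: n = 92 planned subjects (SAP 1), and the interval named in SAP 7.7.2. The exact one-sided 97.5% lower bound for x successes in n is the 0.025 quantile of Beta(x, n − x + 1), which equals 0.025^(1/n) when x = n. Let a be the failures counted as successes (row 1) and b the failures dropped (rows 2 and 3), with everyone else a success. As written, the rate is (92 − b)/(92 − b). Aligned with the primary endpoint, it is (92 − a − b)/92.

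| a | b | As written | Lower bound | Aligned | Lower bound |
|---|---|---|---|---|---|
| 0 | 0 | 92/92 = 100% | 96.1% | 92/92 = 100% | 96.1% |
| 0 | 2 | 90/90 = 100% | 96.0% | 90/92 = 97.8% | 92.4% |
| 2 | 0 | 92/92 = 100% | 96.1% | 90/92 = 97.8% | 92.4% |
| 1 | 1 | 91/91 = 100% | 96.0% | 90/92 = 97.8% | 92.4% |
| 2 | 2 | 90/90 = 100% | 96.0% | 88/92 = 95.7% | 89.2% |
| 4 | 4 | 88/88 = 100% | 95.9% | 84/92 = 91.3% | 83.6% |

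In this setting each affected subject is worth 1/92, about 1.1 percentage points. The values of a and b are assumptions.

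**Step 3: the opposite direction.** If PP contains two failures and the wait or monitoring rule removes two successes, 90/92 = 97.83% becomes 88/90 = 97.78%. Those exclusions can therefore lower the rate slightly.

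**The case against.** The defence has several sound parts.

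- **No conflict of definition between documents.** The SAP repeats the protocol's definition, and Protocol 18.9.5 also places secondary effectiveness in PP. An endpoint of pure electrical isolation beside a composite primary is a legitimate choice. This stands. However, Protocol 18.6 defines PP without the major-deviation exclusions. Those are SAP additions, and they make the set depend on procedural compliance and later follow-up.
- **The SAP does not say it counts non-study catheter isolation.** A reader might infer an explicit rule. In fact the SAP is silent, and the success follows only because nothing excludes it. A subject treated solely with another catheter is outside PP.
- **Unconfirmed block is not a PP exclusion.** A reader might infer that everyone without confirmation leaves the denominator. The listed deviations concern the wait and the drug challenge. The clause can even be read as covering only subjects whose block was confirmed without them, so loss of abandoned procedures is possible, not certain. Nor does SAP 7.1, with "Percentages will be based on the number of subjects without missing data", clearly remove such subjects: where the endpoint is confirmation itself, absence of confirmation is more naturally an unmet endpoint than a missing value.
- **Not every exclusion inflates the rate.** Skipping the wait is not a primary acute failure, and the monitoring rule ignores the acute result. A claim of uniform upward bias is not supported.
- **Consequence.** There is no test and no goal. Acute failures remain in the primary analysis through mITT, SAP 7.7.2 reports a QMODE+-only isolation rate, and SAP 7.7.3 summarises devices used.

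These points limit the size of the problem. They do not remove the double classification in row 1 or the certain loss in row 2.

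**Conclusion.** The point holds as a matter of definition and analysis set. A subject whose veins were completed with a non-study catheter can be a primary acute failure and a secondary acute success. The PP set cannot contain catheter-related discontinuations. It can lose unconfirmed procedures, and it drops subjects with no rhythm monitoring whatever their result on the day.

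Catheter-related discontinuations, and any unconfirmed procedures that leave PP, push the rate upward. The wait and monitoring exclusions can also remove successes, so their net direction is not fixed.

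Two affected subjects would move the rate by about 2 points and the lower bound by about 4 (92.4% against 96.0% or 96.1%). That rests on assumed counts, on no other failures, and on 92 treated. Because 92 is planned enrolment and enrolment means consent (Protocol 9.5), the treated number may be lower.

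A reader might infer that trial success is affected. It is not: the endpoint is descriptive, and study success, alpha and power are unchanged.

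**What to change.** In SAP 7.7.2:

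1. State that use of a non-study catheter on a pulmonary vein target is a failure for acute procedural success. Do not extend this to the cavo-tricuspid isthmus, which is not part of a vein-isolation endpoint.
2. Report the rate and its 97.5% lower bound in the mITT set, counting unconfirmed entrance block and catheter-related discontinuation as failures. A set restricted to RF-treated subjects would still omit those discontinuations. Keep SAP 5's rule that discontinuations unrelated to the catheter are not failures, and say whether those subjects stay in the denominator.
3. Keep the PP rate as a supportive analysis.

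The cost is SAP wording and one further table. Non-study catheter use is already recorded under Protocol 13.5. The reported rate may be slightly lower.

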	Incidence of Unanticipated Adverse Device Effects (UADEs)	
Secondary Endpoints & Follow- up Intervals	• Incidence of Serious Adverse Events (SAEs) within 7 days (early onset), >7 to 30 days (peri-procedural) and >30 days (late onset) of initial ablation	
	• Incidence of bleeding complication: a) Major, b) clinically relevant non-major and c) minor bleeding as defined in the 2017 HRS/EHRA/ECAS/APHRS /SOLAECE Consensus Statement	
	Secondary Effectiveness Endpoints:	
	Acute Procedural success:	
	
 
% of subjects with electrical isolation of all PVs (entrance block) at the end of the procedure
 
	
	
 
The % of subjects with electrical isolation of PVs (entrance block) using QMODE+ as only ablation strategy
 
	
	
 
% of subjects with electrical isolation of all PVs (entrance block) after first encirclement (evaluated prior to the 20-minute waiting period and adenosine challenge)
 
	
	
 
% of subjects with electrical isolation of all PVs (entrance block) after first encirclement without acute reconnection, after waiting period and adenosine challenge
 
	
	• % of subjects and % of PVs with touch-up (ablation of acute reconnection) among all targeted veins and touch-up location	
	
 
Anatomical location of acute PV reconnection after first encirclement
 
	
	Repeat Ablation Procedures:	
	
 
Incidence (%) of repeat ablation procedures during 12-months period post-procedure
 
	
	$\circ$ % PVs re-isolated among all of the targeted PVs at repeat procedure	
	
 
% repeat ablation procedures requiring new linear lesions and/or identifying new foci outside of initially isolated area among the
 
	

	repeat ablation procedures
	12-Month Single Procedure Success
	
 
o The 12-month single procedure success is defined as freedom from documented AF/AFL/AT recurrence (episodes ≥ 30 secs) during the Evaluation Period after a single ablation procedure and off AADs. Any repeat ablation procedure or AAD therapy will be deemed effectiveness failure for this analysis
 

	Additional Endpoints:
	Procedural data
	• total procedure time, PVI time, RF application time, mapping time, and RF application time per lesion
	
 
fluoroscopy time/dose
 

	
 
location of RF applications, number of RF applications
 

	• RF ablation parameters per application
	
 
Total fluid/irrigation delivered
 

	• Esophageal monitoring

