### 7.2 Objectives

The primary objective of this clinical investigation is to demonstrate the safety and 12month effectiveness of the QDOT MICROTM catheter when used with the nMARQTM RF generator for pulmonary vein isolation (PVI) in the treatment of subjects with paroxysmal atrial fibrillation (PAF).

- To demonstrate the safety based on the proportion of subjects with early-onset (within 7 days of ablation procedure) primary adverse events
- To demonstrate the 12-month effectiveness based on the proportion of subject with freedom from documented atrial arrhythmia (atrial fibrillation (AF), atrial tachycardia (AT) or atrial flutter (AFL)) episodes during the effectiveness evaluation period (Day 91-365)

The major secondary objectives of this study are:

- To evaluate the incidence of (serious) adverse events during and after procedure up to 3 months following procedure.
- To evaluate Acute Procedural Success as defined by:
  - $\circ~$  The % of subjects with electrical isolation of PVs (entrance block) at the end of the procedure, and
    - The % of subjects with electrical isolation of PVs (entrance block) using QMODE+ as the only ablation strategy
    - The % of subjects with electrical isolation of PVs (entrance block) at all power settings combined
  - The % of subjects with electrical isolation of PVs (entrance block) after first pass isolation, after waiting period and adenosine challenge

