### **13.3.2** General AF Procedure Guidelines for QMODE+

The AF ablation procedures for this study should follow the sequence below:

- Diagnostic catheter placement
- Electrophysiology study (discretion of investigator)
- Cardioversion if subject is in AF (discretion of investigator)
- CARTO® Respiratory Gating Mandatory (unless using Jet Ventilation)
- Placement of esophageal temperature monitoring device

- Confirmation of ACT in  $\geq$  350 sec. PRIOR to insertion of the QDOT MICROTM Catheter into the left atrium and maintained throughout the procedure
- Transseptal puncture
- A left atrial anatomical map is required prior to an ablation procedure in the LA.
  - An anatomical map is not required of triggers outside of the left atrium e.g. SVC/CS etc.
- Introduction of the QDOT MICROTM Catheter
  - $\circ~$  Use the AUTOTAG feature in Carto to tag each QMODE+ ablation point after each application
  - $\circ\,$  At the new location ensure catheter stability before commencing RF application.
  - $\circ~$  A pre-ablation flow rate delay of minimal 2 seconds will occur before RF application
  - $\circ$  Ablation: RF power application of up to 90W for up to 4 seconds (QMODE+)
  - Move the catheter to a new location (~4mm) if clinically effective ablation is achieved
  - QMODE+ should be used for full PV encirclement. If the investigator deems QMODE+ unable to achieve PVI, the study catheter in QMODE should be used to complete the procedure (refer to Appendix B for details).
  - Continue RF applications and catheter movement until the circumferential PVI is completed.
  - Precautions:
    - If the temperature increases above the temperature cutoff (default 65°C), RF application will stop immediately (automatically)
    - The decision to interrupt RF power delivery at any time during ablation should be guided by Clinical Investigator judgment and the monitoring of ablation effectiveness parameters commonly used such as catheter movement, EGM reduction and/or impedance changes.
    - For ablation in the region of the right superior PV, precautionary measures such as pacing maneuvers are recommended to evaluate proximity to the phrenic nerve.
- Left Atrial ablation and real time PV isolation
- Post ablation a 20-min waiting period is **REQUIRED** before pacing procedure(s) and/or infusion of cardiac medications to induce AF/reconnection (e.g., Adenosine, Isoproterenol 2-20 mcg/min)

Biosense Webster, Inc 8, 2021 CONFIDENTIAL

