= number of targeted veins reaching PVI prior to 20 – min waiting period total number of targeted veins

• Rate of PVI achieved prior to 20-min waiting period among subjects:

number of subjects reaching PVI prior to 20 – min waiting period total number of subjects who underwent ablation procedure

• PV isolation after first encirclement without acute reconnection (evaluated after waiting period and adenosine challenge)

Percent of subjects and percent of targeted PVs where PVI was achieved after the adenosine challenge and with no additional RF applications to remove PV reconnection will be summarized descriptively.

• Rate of PVI achieved after adenosine challenge among targeted veins:

 $number\ of\ targeted\ veins\ reaching\ PVI\ after\ adnosine\ challenge\ and\ without\ acute\ reconnection$

• Rate of PVI achieved after adenosine challenge among subject:

= number of subjects reaching PVI after adenosine challenge and without acute reconnection total number of subjects who underwentblation procedure

o Acute PV reconnection after first encirclement

Percent of subjects and percent of targeted PVs where PV reconnection was observed after the adenosine challenge will be summarized descriptively.

• Rate of acute PV reconnection among targeted veins:

= number of targeted veins with PV reconnection after adenosine challenge total number of targeted veins

Rate of acute PV reconnection among subject:

= number of subjects with PV reconnection after adenosine challenge total number of subjects who underwent ablation procedure

• PVs with touch-up (i.e. touch-up or ablation for acute reconnection)

Percent of subjects and percent of targeted PVs where additional RF applications was applied to remove PV reconnection, regardless the timing of PVI or the confirmation of the entrance block, will be summarized descriptively.

Rate of PV touch-up among targeted veins:

 $= \frac{number of targeted veins with touch - up RF application}{total number of subjects who underwent ablation procedure}$

• Rate of PV touch-up among subjects:

 $= \frac{number of subjects with touch - up RF application}{total number of subjects who underwent ablation procedure}$

• Repeat ablation procedures during 12-month period post procedure

• Rate of repeat procedures

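### The numerator for isolation after first encirclement in SAP 7.7.2 tests timing only, so it can count veins that the first encirclement did not isolate

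*SAP*

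**What the plan says.** The Protocol Summary (4.0) describes the endpoint as entrance block in all PVs "after first encirclement (evaluated prior to the 20-minute waiting period and adenosine challenge". Protocol 8.2.3.2 lists it again as the percentage "of subjects with electrical isolation of PVs (entrance block) after first encirclement". It sets two conditions: what had been done (one encirclement) and when the vein was checked (before the wait). Neither place makes an allowance for extra applications. The related objective in Protocol 7.2, which concerns the check made after the wait, speaks of isolation "after first pass isolation, after waiting period and adenosine challenge".

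SAP 7.7.2 carries the name over as "PVs isolation after first encirclement (evaluated prior to the 20-minute waiting period and adenosine challenge". The definition beneath it takes in every subject and vein isolated by the time the wait begins, and adds the clause "regardless the additional application was applied to remove the PV reconnection or not". The subject formula has the numerator "number of subjects reaching PVI prior to 20 – min waiting period", and the vein formula has the same form.

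Three procedural statements bear on this:

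- Protocol 13.4 starts the 20-minute wait at the last RF application to a PV.
- Protocol 13.3.2 tells the operator: "Continue RF applications and catheter movement until the circumferential PVI is completed".
- Protocol 13.3.1 and 13.3.2 have the operator use QMODE to complete the procedure when QMODE+ is judged unable to achieve PVI.

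SAP 7.7 makes all secondary endpoints descriptive, with no hypothesis test. The secondary effectiveness endpoints are summarised in the Variable Flow per-protocol set.

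**The concern.** The SAP's definition and formulas keep the timing condition and drop the encirclement condition. Extra applications needed to reach isolation come before the wait by design, because the wait starts only after the last application. Timing therefore cannot separate a vein isolated by the first circle from one isolated by later gap applications or by a change of mode.

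What is at stake is the interpretation of one secondary result. SAP section 1 says the Variable Flow results will be used for additional claims about the safety and effectiveness of the variable flow feature. A rate labelled first encirclement that includes veins completed afterwards would not support a statement about first-encirclement performance.

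**Working it through.** The documents state no expected or target rate for this endpoint, so there is no figure to reproduce. The check compares definitions.

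**Step 1. Follow three kinds of vein through the definitions, read literally.**

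- Vein A is isolated by the first circle and stays isolated.
- Vein B is isolated by the first circle, reconnects on the challenge and is touched up.
- Vein C is not isolated by the first circle. Further applications isolate it before the wait, and it does not reconnect.

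| Measure | A | B | C |
|---|---|---|---|
| Protocol endpoint: isolated after first encirclement, checked before the wait | yes | yes | no |
| SAP numerator: reaches PVI before the wait | yes | yes | **yes** |
| SAP companion: isolated after the challenge, no RF for reconnection | yes | no | **yes** |
| SAP touch-up: RF applied to remove reconnection | no | yes | no |
| SAP PVI at end of procedure | yes | yes | yes |

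The protocol endpoint and the SAP numerator disagree only on vein C. No other measure in this group isolates vein C. The companion and touch-up measures concern applications that remove reconnection, and vein C has not reconnected. The QMODE+-only rate would drop vein C if QMODE closed the gap, but not if more QMODE+ applications did.

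**Step 2. Size.** Let f be the share isolated by the first encirclement alone. Let g be the share of the remainder isolated by further applications before the wait. The documents give neither.

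- Rate under the protocol's name: f
- Rate under the SAP numerator: f + (1 − f) × g
- Overstatement: (1 − f) × g

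The overstatement is 0 when g = 0. It is 1 − f when g = 1, and the SAP rate is then 100% whatever f is. Illustration with an assumed g = 0.95:

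| f (assumed) | SAP rate | Overstatement |
|---|---|---|
| 0.70 | 0.70 + 0.30 × 0.95 = 98.5% | 28.5 points |
| 0.80 | 0.80 + 0.20 × 0.95 = 99.0% | 19.0 points |
| 0.90 | 0.90 + 0.10 × 0.95 = 99.5% | 9.5 points |

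If all 92 planned Variable Flow subjects were analysed, the first row would be about 91 subjects (92 × 0.985 = 90.6) against about 64 (92 × 0.70 = 64.4). The per-protocol set may be smaller.

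The illustration shows that when g is high, the reported rate hardly responds to f. It does not show that g is high in this trial.

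**The case against.** The strongest objection concerns the clause "regardless the additional application was applied to remove the PV reconnection or not". A reader might infer that it expressly admits any extra application used to close the first circle. The documents do not support that. The clause speaks of removing reconnection, and a vein never isolated cannot reconnect. SAP 7.7.2 measures reconnection after the adenosine challenge and lists RF for reconnection as a time point separate from the one before the wait. The clause may therefore mean only that vein B still counts, which fits the protocol's pairing of one measure before the wait with another after it. In the other direction, the SAP's touch-up measure applies whatever the timing of PVI. This stands as an ambiguity, but the point rests on the numerators, which test timing alone under either reading.

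A second objection is that the SAP heading still names the first encirclement, so the text below may only be fixing the time of evaluation. That reading is available. A programmer following the printed formulas would nevertheless not apply it.

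Third, the instruction "Continue RF applications and catheter movement until the circumferential PVI is completed" can be read as finishing the circle rather than closing gaps in it. That is fair. Protocol 13.4, on when the wait starts, and 13.3.1, on using QMODE to complete the procedure, are the firmer evidence.

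Finally, a reader might infer that the rate will be near 100% by construction, or overstated by 10 to 30 points. Neither follows. Both depend on shares that the documents do not state.

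**Conclusion.** The point holds as a mismatch between the endpoint's name and its numerator. As written, SAP 7.7.2 can count veins or subjects isolated before the wait by applications made after the first encirclement. The overstatement is (1 − f) × g, which lies between 0 and 1 − f, and the documents supply neither quantity.

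This rests on reading the formulas literally. If the heading is meant to restrict them, the remedy is simply to say so. The documents do not support the stronger statement that the rate cannot measure first-encirclement isolation at all: the two coincide when no vein needs further applications before the wait.

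The consequence is minor. The endpoint is descriptive and untested, and it does not enter the primary endpoints, the sample size or the type I error.

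**What to change.** In SAP 7.7.2, count a targeted vein only if entrance block is present on completion of the first encirclement and no further RF is applied to that vein before the 20-minute wait. Count a subject only if all targeted veins meet this. Report the present measure on its own line as PVI before the waiting period. State whether the clause on additional applications refers to touch-up after the wait, before it, or both. Nothing in the procedure needs to change.

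The cost is mainly SAP wording, but it should not be assumed that the data are ready. Protocol 13.5 lists application parameters with location and mode, touch-up applications, and CARTO and generator files. It does not list a field for entrance block at the end of the first circle, and the protocol ties touch-up to acute reconnection. That list is not exhaustive, so the sponsor should confirm that the end of the first encirclement, and the isolation status then, can be identified. Some derivation may be needed, and the reported rate may be lower.
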